AUC	Area under the plasma concentration-time curve					
AUC _{0-t}	Area under the plasma concentration-time curve up to the last measured time point					
AUC _{0-∞}	Area under the plasma concentration-time curve extrapolated to infinite time					
AUC_%Extrap_obs	Percentage of AUC that is extrapolated					
AxMP	Auxiliary medicinal product					
BE	Bioequivalence					
BMI	Body mass index					
CDSCO	Central Drugs Standard Control Organization					
CIOMS	Council for International Organizations of Medical Sciences					
Cmax	Maximal (peak) plasma concentration					
COA	Certificates of analysis					
COVID-19	Coronavirus Disease 2019					
CPMS	Clinical Pharmacology Modeling and Simulation					
CPSB	Consumer Product Safety Board					
CRF/eCRF	Case report form/electronic case report form					

TMF-16298784 Protocol Versio						
Abbreviation	Definition					
CSI	Core safety information					
CSR	Clinical study report					
CV	Cardiovascular					
CV_W	Coefficient of variation					
CV%	Intra-subject variability					
ECG	Electrocardiogram					
ED	Early discontinuation					
EoS	End-of-study					
FDA	Food and Drug Administration, United States of America					
FSH	Follicle stimulating hormone					
FSFV	First subject first visit					
GAELF	Global Alliance to Eliminate Lymphatic Filariasis					
GCP	Good clinical practices					
GDS	Global Data Sheet					
GLM	General linear model					
GMO	Genetically modified organism					
GMP	Good manufacturing practice					
GMR	Geometric mean ratio					
HCV	Hepatitis C virus					
HbsAg	Hepatitis B surface antigen					
HIPAA	Health Insurance Portability and Accountability Act					
HRT	Hormonal replacement therapy					
ICF	Informed consent form					
ICH	International Council on Harmonisation					

Abbreviation	Definition Protocol Version No. 1.0				
Abbieviation					
ICMJE	International Committee of Medical Journal Editors				
ICMR	Indian Council of Medical Research				
IDFU	Investigational directions for use				
IEC	Independent ethics committee				
IM	Intramuscular				
IMP	Investigational medicinal product				
IMPD	Investigational medicinal product dossier				
IND	Investigational New Drug				
IRB	Institutional review board				
λ_z	Slope of the (terminal) log-lin phase of the plasma concentration-time curve				
LAR	Legally acceptable representative				
LSLV	Last Subject Last Visit				
MDA	Mass drug administration				
MSR	Medical Screening Record				
NIMP	Non-investigational medicinal product				
NQ	Non-quantifiable				
OTC	Over the counter				
POAP	Pregnancy Outcome Advisory Panel				
POM	Prescription only medicine				
PK	Pharmacokinetic				
PP	Per protocol				
QTL	Quality tolerance limit				
SADE	Serious adverse device effect				

11011 - 10290704	FIGURE VERSION NO. 1.0			
Abbreviation	Definition			
SAE	Serious adverse event			
SAP	Statistical analysis plan			
SCABE	Scaled average bioequivalence			
SoA	Schedule of activities			
SOP	Standard operating procedure			
SRT	Safety Review Team			
σ_{WR}	Within-subject standard deviation			
TEAE	Treatment-emergent adverse event			
T _{max}	Time of peak concentration			
TOC	Table of contents			
TOST	Two one-sided t-test			
T _{1/2}	Half-life			
USA	United States of America			
USADE	Unanticipated serious adverse device effect			
WBC	White blood cell			
WHO	World Health Organization			
WOCBP	Woman of childbearing potential			
WONCBP	Woman of nonchildbearing potential			

TMF-16298784	Protocol Version No. 1.0
Term	Definition
Certified copy	A copy (irrespective of the type of media used) of the original record that has been verified (i.e. by a dated signature or by generation through a validated process) to have the same information, including data that describe the context, content, and structure, as the original.
Combination product	Combination product comprises any combination of
	– drug
	- device
	 biological product
	Each drug, device and biological product included in a combination product is a constituent part.
Decentralized Trial Platform	A digital engagement technology allowing for the remote delivery and access to trials for sponsors.
Eligible	Qualified for enrollment into the study based upon strict adherence to inclusion/exclusion criteria.
Essential documents	Documents which individually and collectively permit evaluation of the conduct of a study and the quality of the data produced
Intervention number	A number identifying an intervention to a participant, according to intervention allocation.
Investigational medicinal	An IMP is a pharmaceutical form of an active substance or placebo being tested or used as a reference in a clinical study, including products already with a marketing authorization but used or assembled (formulated or packaged) in a way different from the authorized form, or when used for an unauthorized indication, or when used to gain further information about the authorized form. Medicinal products with a marketing authorization are IMPs when they are to be used as the test substance, reference substance, or comparator in a clinical study, provided the requirement(s) in the definition is/are met.
Investigator	A person responsible for the conduct of the clinical study at a study site. If a study is conducted by a team of individuals at a study site, the investigator is the responsible leader of the team and may be called the principal investigator.

TMF-16298784	Protocol Version No. 1.0
Term	Definition
	The investigator can delegate study-related duties and functions conducted at the study site to qualified individual or party to perform those study-related duties and functions
Legally acceptable representative	An individual, judicial or other body authorized under applicable law to consent on behalf of a prospective participant to the participant's participation in the clinical study.
	The terms legal representative or legally authorized representative are used in some settings.
NIMP/AxMP	A NIMP or AxMP is a medicinal product that is not classified as an IMP in a study, but may be taken by participants during the study, e.g., concomitant or rescue/escape medication used for preventive, diagnostic, or therapeutic reasons or medication given to ensure that adequate medical care is provided for the participant during a study.
Participant number	A unique identification number assigned to each participant who consents to participate in the study.
Participant	Term used throughout the protocol to denote an individual who has been contacted to participate or who participates in the clinical study as a recipient of the study intervention (vaccine(s)/product(s)/control).
	Synonym: subject
Randomization	Process of random attribution of intervention to participants to reduce selection bias.
Self-contained study	Study with objectives not linked to the data of another study.
Source data	All information in original records and certified copies of original records of clinical findings, observations, or other activities in a clinical study necessary for the reconstruction and evaluation of the study. Source data are contained in source documents (original records or certified copies).

11011 - 10230704	1 Totocol Version No. 1.0			
Term	Definition			
Study intervention	Term used throughout the clinical study to denote a set of investigational product(s) or marketed product(s) or placebo intended to be administered to a participant. Note: "Study intervention" and "study treatment" are used interchangeably unless otherwise specified.			
Study completion date	The date on which the last participant in a clinical study was examined or received an intervention/treatment to collect final data for the primary outcome measures, secondary outcome measures, and AEs (that is, the last participant's last visit or LSLV).			
Study monitor	An individual assigned by the sponsor and responsible for assuring proper conduct of clinical studies at 1 or more investigational sites.			

Protocol Version No. 1.0

1. PROTOCOL SUMMARY

1.1. Synopsis

Protocol Title: An Open Label, Balanced, Randomized, Two-Treatment, Four-Period, Two-Sequence, Single Oral Dose, Full Replicate Crossover, Bioequivalence Study of Albendazole Tablets IP 400 mg of Biddle Sawyer Limited (GSK group company) with Albendazole Tablets 400 mg of Glaxo SmithKline Consumer Healthcare, South Africa (PTY) Ltd in Healthy, Adult participants under Fed Condition.

Brief Title: Bioequivalence study between two albendazole 400 mg tablets in healthy, adult participants under fed conditions.

Rationale: Refer to Section 2.1.

Objectives, Endpoints, and Estimands: Refer to Section 3.

Overall Design: Refer to Section 4.1.

[figure not shown]
Number of Participants: Refer to Section 9.6.

Data Monitoring/Other Committee: Refer to Section 10.1.6.

1.2. Schema

Based on US FDA guidance, this study will employ 2 sequences in a 4-period cross-over design, i.e. T-R-T-R and R-T-R-T (T=test study intervention, R=reference study intervention).

Figure 1 Study design overview

1.3. Schedule of activities (SoA)

Table 1 Schedule of Activities – Overview Across Periods

Procedure	Screening (up to 28 days before Dosing in period I)		Period I		Period II, III and IV			ED = early discontinuation / withdrawal	Reference section	
Day		-1	1	2	-1	1	2			
Informed consent	(Consent for screening)	(Study specific consent)							[See Section 10.1.3 for details]	
Inclusion and exclusion criteria		•							[See Section 5.1 and Section 5.2 for Inclusion and Exclusion criteria]	
Demography	•								[See Section 8.1.1 for more information]	
Compliance Assessment		•			•				[See Section 5.3.1, Section 5.3.2 for more information]	
Height and weight	•								[See Section 8.3.1 for more information]	
Physical examination/ clinical examination	•	•		•	•		•		[See Section 8.3.1 for more information]	
Medical history	•								[See Section 8.1.2 for more information]	
Urine Drug Screening, breath alcohol Test	•	•			•				Substances: [Drugs, Alcohol, tobacco and caffeine]	

Procedure	Screening (up to 28 days before Dosing in period I)		Period I Period II, III and IV		ED = early discontinuation / withdrawal	Reference section			
Day		-1	1	2	-1	1	2		
Serum Pregnancy Test (for females only)	•	•			•		*	•	[See to Section 8.3.5— pregnancy testing for instruction on timepoints]
Serology Tests [HIV, Hepatitis B and C screening]+	•								[See Section 8.3.4, Section 10.2 for more information]
Laboratory assessments +	•				•		*	•	[See Section 8.3.4, Section 10.2 for more information]
12-lead ECG	•								[See Section 8.3.3 for more information]
Chest X-ray\$	•								[See Section 8.3.1 for more information]
Pre dose vital signs			•			•			[See Section 8.3.2 for more information]
Post dose Vital signs%			•			•			[See Section 8.3.2 for more information]
Check-in		•			•				
Administration of study intervention			•			•			[See Section 6.1 for more information]
Blood Collection for PK Analysis #			•	•		•	•		[See Section 8.5 for more information]

Protocol Version No. 1.0

TMF-16298784

Procedure	Screening (up to 28 days before Dosing in period I)	Period I		Period II, III and IV		ED = early discontinuation / withdrawal	Reference section		
Day		-1	1	2	-1	1	2		
AE review			•	•	•	•	•		[See Section 10.3.5, Section 8.4 for more information]
SAE review		•	•	•	•	•	•		[See Section 10.3.5, Section 8.4 for more information]
Concomitant medication review			•	•	•	•	•		[See Section 6.9 for more information]

HIV: human immunodeficiency virus, ECG: electrocardiogram, PK: pharmacokinetic, AE: adverse event, SAE: serious adverse event, (e)CRF: (electronic) case report form

- Is used to indicate a study procedure that requires databasing (either in eCRF, device, laboratory or other third-party vendor).
- * End study safety assessment (i.e. at the time of check-out of period IV)
- + Clinical Laboratory tests will be performed as per Section 10.2: Clinical laboratory tests (Meals will be provided to the participants as mentioned in the protocol)
- \$ Chest X-ray is valid up to 6 months including the day of first dosing.
- # The venous blood samples will be drawn at 0.00 (Pre-dose) and at 0.33 (0h20min), 0.67 (0h40min), 1.00 (1h00min), 1.33 (1h20min), 1.67 (1h40min), 2.00 (2h00min), 2.33 (2h20min), 2.67 (2h40min), 3.00 (3h00min), 3.33 (3h20min), 3.67 (3h40min), 4.00 (4h00min), 4.50 (4h30min), 5.00 (5h00min), 8.00 (8h00min), 10.00 (10h00min), 12.00 (12h00min), 14.00 (14h00min), 18.00 (18h00min), 24.00 (24h00min) post dose in each period.

 %Post-dose vitals will be recorded at 2, 4, 6, 12 and 24 hours post-dose in each period.
- Check-in day (Day -1)
- Dosing Day (Day 1)
- Housing Day (Day -1 to 2)
- Check-out Day (Day 2, morning)
- End Study (i.e. at the time of check-out of period IV)

Table 2 Schedule of Activities – Detailed View within Period

Procedures												
Time (h) in relation to albendazole dose	0 (Pre-dose)	0.33, 0.67, 1.00, 1.33, 1.67	2.00	2.33, 2.67, 3.00, 3.33, 3.67	4.00	4.50, 5.00,	6.00	8.00, 10.00	12.00	14.00	18.00	Next day 24.00 (Discharge)
AE/SAE assessment	│										—	
Vital signs			Χ		Χ		Х		Х			Х
Blood collection for PK Analysis	Х	Χ	Х	Х	Χ	Х	Х	Х	Х	Х	Χ	Х
Discharge												Х

PK: pharmacokinetic, AE: adverse event, SAE: serious adverse event

2. INTRODUCTION

2.1. Study rationale

This study is being conducted to address the World Health Organization (WHO) Medicines prequalification requirements for the registration of an albendazole formulation, to be provided to the WHO global health program, manufactured at a new facility. Its primary aim is to assess the bioequivalence between the Sponsor's test study intervention and the reference study intervention after single oral dose administration in healthy adult participants under fed conditions. In addition, it compares the pharmacokinetic profile and safety between test and reference intervention. The current product being provided to WHO as part of the global health program was chosen as the comparator (reference) product. This product is comparable to the product marketed in regulated countries (Zentel, Eskazole) with respect to formulation, manufacturing process, site of manufacture, and methods with the exception of the addition of a colouring agent in the product formulation.

2.2. Background

Albendazole is a benzimidazole carbamate with antiprotozoal and anthelmintic effects against intestinal and tissue parasites. Albendazole exhibits larvicidal, ovicidal and vermicidal activity, and it is thought to exert its anthelmintic effect by inhibiting tubulin polymerization. This causes the disruption of the helminth metabolism, including energy depletion, which immobilizes and then kills the susceptible helminth.

Pharmacokinetics:

In humans, albendazole is poorly absorbed (less than 5%) following oral administration, but its absorption is greatly enhanced (approximately 5-fold) when taken with fat-rich food. After absorption, albendazole rapidly undergoes extensive first-pass metabolism in the liver resulting in several metabolites of which albendazole sulfoxide is its main metabolite.

Peak concentrations are achieved for albendazole approximately 2 hours after dose, and for albendazole sulfoxide approximately 4 hours after dose. The $T_{1/2}$ of albendazole is approximately 1.5 hours and for albendazole sulfoxide 8.5 hours.

For gastro-intestinal infections, the parent compound albendazole is considered the active moiety, whereas for systemic infections this is albendazole sulfoxide. For the purpose of determining bioequivalence, however, the WHO requires this to be shown for the albendazole parent compound.

2.3. Benefit/risk assessment

Participation in bioavailability studies yields no direct benefit to the participants. However, a charge-free study related health assessment is provided. The risks as described below are reduced considering the fact only 4 doses are to be administered at an interval of at least 7 days between dosing days of any 2 successive periods.

Table 3 Potential risks and risk mitigation strategies

The potential risks of clinical significance for albendazole tablets are derived from the prescribing information (Albendazole label). Most of these reported risks are uncommon, rare or very rare. The likelihood of these risks in a healthy population receiving a single dose is therefore expected to be low. For complete list of adverse reactions please refer the prescribing information mentioned above.

Potential Risk of Clinical Significance	Summary of Data/Rationale for Risk	Mitigation Strategy
	Study Intervention(s)	
Hepatotoxicity	In 2001, GSK routine monitoring of spontaneous ADRs identified an increased number of reports of elevated liver enzymes in patients receiving low dose albendazole and reports of hepatitis and jaundice in patients receiving high dose albendazole. Higher doses of albendazole are used to treat systemic helminth infections for longer periods compared to the low dose, short treatment durations required for intestinal helminth infections in the OTC environment. A cumulative review of hepatic events was conducted to further evaluate the nature of these events and to determine whether GSK's CSI adequately reflected these adverse events. Following the review of the available data, GSK concluded that there was sufficient evidence to suspect albendazole as causing hepatic events; with low dose albendazole causing	This study will not include participants with abnormal liver function test results (transaminases). Discontinuation of study intervention in the best interest of the participant for abnormal liver tests at the investigator discretion, when liver parameter falls outside the pre-defined clinically acceptable values. If any participant has clinically significant abnormal liver function analysis during the study, in such case participant may be discontinued for specific period at the investigator discretion. The decision to continue/discontinue such participants will be based on investigator's decision.

Protocol Version No. 1.0

Detential Diely of Clinian	Summaria of	Mitigation Stratogy		
Potential Risk of Clinical	Summary of Data/Rationale for Risk	Mitigation Strategy		
Significance	Data/Kationale for Kisk			
	elevation of liver enzymes and the high dose use causing hepatitis. The CSI for POM albendazole global data sheet (GDS) was therefore updated to include these events in the Adverse Reactions section as well as appropriate warnings in the Dosing and Administration and Warnings and Precautions sections			
Exposure during pregnancy	Pre-Clinical Data in common with other benzimidazole compounds, administration of albendazole to pregnant animals can cause abnormalities of foetal development, including increased embryo resorption, soft tissue malformation and skeletal deformities. This teratogenic and embryotoxic activity has led to the recommendation that albendazole must not be prescribed to females who are pregnant. Post marketing surveillance in 2012, the GSK POAP reviewed all relevant new data in a context specific manner with a view to providing an assessment on the use of albendazole (and mebendazole another benzimidazole, which is structurally and physiologically similar to albendazole) for the treatment of intestinal	Albendazole is contraindicated in pregnancy and should not be administered during pregnancy or in women thought to be pregnant. Pregnant women will not be included. Serum Pregnancy test for female participants will be done at the time of screening, prior to check-in of each period and at the end of the study (at the time of check-out of period IV). Pregnancy testing must be done even if the participant is menstruating at the time of the study visit. The study intervention may only be administered if the pregnancy test is negative. For female participants history of menstruation and use of contraceptive methods will be evaluated by trained study physician at the time of screening.		

Protocol Version No. 1.0

Potential Risk of Clinical	Summary of	Mitigation Strategy		
Significance	Data/Rationale for Risk	→ ·····• √		
	infections during various exposure scenarios in pregnancy. POAP considered the Weight-of-Evidence of all the reported pregnancy outcomes relative to all trimesters of pregnancy. The data reviewed included 16 publications (including meta-analyses) involving drug exposures to over 12,000 pregnant women (albendazole: N=6000; mebendazole: N=6000). Subsequent to the POAP consultation on the use of albendazole during pregnancy, the GSK CPSB decided that there was insufficient evidence to remove the contraindication regarding use during pregnancy in the OTC setting	Female participants who become pregnant after the first study intervention dose must not receive subsequent doses of the study intervention and will be withdrawn from the study.		
Neurological disorders	The neurological disorders include headache and dizziness are listed in the adverse reaction section.	Considering single oral dose of albendazole with 1-week interval between the doses, headache and dizziness subsides on its own before the next period starts. If these symptoms continue during II, III and IV period admission, withdrawal of participant can be considered based on principal investigator decision and condition of participant.		

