5. STUDY POPULATION

Prospective approval of protocol deviations to recruitment and enrollment criteria, also known as protocol waivers or exemptions, is not permitted.

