5.1. Inclusion criteria

Participants are eligible to be included in the study only if all of the following criteria apply:

- a) Non-smoker, healthy, adult human participants between 18 to 45 years of age (both inclusive).
- b) Having a BMI between 18.5 to 30.0 (both inclusive), calculated as weight in kg/height in m².
- c) Not having any significant diseases or clinically significant abnormal findings during screening, medical history, clinical examination, laboratory evaluations, 12-lead ECG and X-ray chest (postero-anterior view) recordings.
- d) Able to understand and comply with the study procedures, in the opinion of the principal investigator.
- e) Able to give voluntary written informed consent for participation in the study.
- f) In case of female participants:
 - Surgically sterilized at least 6 months prior to study participation;

Or

If of childbearing potential is willing to use a suitable and effective double barrier contraceptive method or intra uterine device during the study.

And

Serum pregnancy test must be negative.

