5.2.1. Medical Conditions

- a) Known hypersensitivity or idiosyncratic reaction to albendazole or any excipients or any related drug or any substance.
- b) History or presence of any disease or condition which might compromise the haemopoietic, renal, hepatic, endocrine, pulmonary, central nervous, cardiovascular, immunological, dermatological, gastrointestinal or any other body system.

221030

TMF-16298784 Protocol Version No. 1.0

- c) Any history or presence of asthma (including aspirin induced asthma) or nasal polyp or NSAIDs induced urticaria.
- d) History or presence of seizure or psychiatric disorders.

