5.2.4. Diagnostic Assessments

- a) A positive hepatitis screen including hepatitis B surface antigen and/or HCV antibodies.
- b) A positive test result for HIV antibody (1 and/or 2).
- c) The presence of clinically significant abnormal laboratory values during screening.

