8. STUDY ASSESSMENTS AND PROCEDURES

• All participants will undergo physical and clinical screening procedure within 28 days prior to the first dose administration. The participant will be selected on the inclusion and exclusion criteria mentioned in Section 5.1 and Section 5.2.

• Study procedures and their timing are summarized in the SoA in Section 1.3 Schedule of activities (SoA). Protocol waivers or exemptions are not allowed.

- Adherence to the study design requirements, including those specified in the SoA, is essential and required for study conduct.
- All screening evaluations must be completed and reviewed to confirm that potential participants meet all eligibility criteria.
- Laboratory parameters obtained during the process of screening will be evaluated as follows:
 - *i*. Out of range values of other hematology and biochemistry parameters and urine parameters will be individually evaluated and / or repeated for their clinical significance. A participant will be enrolled into the study only if the medically qualified reviewer deems the values clinically insignificant or acceptable.
 - ii. All immunology parameters are required to be negative.
 - iii. Serum Pregnancy test for females will be negative

(Note: In case if any extra tests are analyzed, it will not have any impact on the trial if the parameters and the values are clinically insignificant.)

- Include the maximum amount of blood collected from each participant over the duration of the study and if any repeat or unscheduled samples may be taken, as appropriate.
- Single oral dose of 1 tablet of either Test study intervention or Reference study intervention (each containing 400 mg of albendazole) will be administered to each participant in each period.

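### Table 3 says volunteers with abnormal transaminases will not be included, but the entry rules bar only clinically significant values and do not apply the Section 10.6 ALT/AST limits

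*Protocol*

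**What the plan says.** **The stated safeguard.** Protocol Section 2.3, Table 3, hepatotoxicity row, opens its mitigation column with "This study will not include participants with abnormal liver function test results (transaminases"). The sentence carries no qualifier and no numeric limit. The same cell then speaks of discontinuation when a liver parameter leaves the pre-defined acceptable range, and of clinically significant abnormal liver results arising during the study.

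**The entry rules.**
- Section 5.1(c) requires "Not having any significant diseases or clinically significant abnormal findings during screening, medical history, clinical examination, laboratory evaluations", among other screening items.
- Section 5.2.4(c) excludes for "The presence of clinically significant abnormal laboratory values during screening".
- Section 5.2.1(b) excludes for "History or presence of any disease or condition which might compromise the haemopoietic, renal, hepatic" or other listed body systems. It concerns a disease or condition and sets no laboratory limit.
- Section 8 states: "The participant will be selected on the inclusion and exclusion criteria mentioned in Section 5.1 and Section 5.2". Item i of the screening laboratory rules then has out-of-range haematology, biochemistry and urine results assessed individually, repeated, or both. Enrolment is allowed only if a medically qualified reviewer finds the values clinically insignificant or acceptable.

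**The numeric limits.** Section 10.6 gives SGPT (ALT) up to 82.0 U/L for men and 56.0 U/L for women, and SGOT (AST) up to 73.0 and 46.0 U/L. The only body text that cites it is Section 7.1.1, on discontinuation.

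**The concern.** *Abnormal* and *clinically significant abnormal* are different tests. A result can be out of range and still be judged of no clinical consequence. The risk table promises the stricter test; the criteria apply the looser one.

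This matters because Table 3 itself reports that the sponsor's review linked low-dose albendazole to raised liver enzymes and puts exclusion at entry first among the mitigations. Participants are healthy volunteers with no direct benefit from dosing. An ethics committee reading Table 3 would believe that people with raised transaminases are kept out, while the criteria as written can let some of them in.

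The Section 5 ban on waivers does not close the gap. It reads "Prospective approval of protocol deviations to recruitment and enrollment criteria, also known as protocol waivers or exemptions, is not permitted", but it protects only the criteria that exist, and none of them contains an ALT or AST limit.

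**Working it through.** No arithmetic applies. The check sets the passages side by side and follows one candidate through them.

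**Step 1: which rules decide entry.** The definitions of terms describe an eligible person as "Qualified for enrollment into the study based upon strict adherence to inclusion/exclusion criteria". Section 8 adds conditions of its own in items i to iii, so the operative rules are 5.1, 5.2 and those items.

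**Step 2: what each rule does with a raised transaminase.**

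| Text | Test applied to screening ALT/AST | Numeric limit |
|---|---|---|
| Table 3, entry sentence | any abnormal result keeps the person out | none given |
| 5.1(c) | clinically significant findings only | none |
| 5.2.4(c) | clinically significant values only | none |
| 5.2.1(b) | hepatic disease or condition, not an enzyme value | none |
| 5.2.4(a) | hepatitis serology, not an enzyme value | not applicable |
| Section 8 item i | out of range is admissible if judged insignificant or acceptable | none |
| 7.1.1 with 10.6 | discontinuation, at the investigator's discretion | ALT 82 (M) / 56 (F); AST 73 (M) / 46 (F) U/L |

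Item i is worded for *other* parameters without saying which ones are set aside, so it does not clearly exempt transaminases.

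**Step 3: one candidate.** Take a man with screening ALT above 82 U/L, no hepatic disease and negative serology, whose result is judged not clinically significant. He meets 5.1(c). He is not excluded by 5.2.1(b), 5.2.4(a) or 5.2.4(c). Item i allows his enrolment. Table 3 says that a person with an abnormal transaminase is not included. The two cannot both hold if *abnormal* means above the Section 10.6 limits.

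**Step 4: the asymmetry.** During the study, a value outside Section 10.6 is a named ground for considering discontinuation (7.1.1). The same value at screening is not a named bar to entry.

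**Step 5: how another Table 3 risk is handled.** Pregnancy is carried into the criteria as a pass/fail rule: 5.1(f) states "Serum pregnancy test must be negative", and Section 8 item iii repeats it. Transaminases have no equivalent rule.

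**The case against.** The best defence is that Section 10.6 is already the screening standard and only a cross-reference is missing. Much of this stands. The appendix sets limits for random glucose, sodium, potassium, chloride, alkaline phosphatase and urinalysis, which Section 8.3.4 and Table 12 schedule only at screening, so those limits have little scheduled use except at entry. Its title concerns clinically acceptable values, and item i uses the word acceptable. The next sentence of the Table 3 cell ties abnormal liver tests to values outside that range. The natural reading is that Section 10.6 is what *abnormal* means. But the Table 3 sentence in question is about discontinuation, and no text applies Section 10.6 to entry, so a reviewer who enrols a candidate above the limits breaks no written rule.

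It can also be said that an enzyme level is continuous and invites judgement, whereas pregnancy and serology tests are read as positive or negative. That is fair, and it weakens the contrast in Step 5. It does not explain why Table 3 makes an unqualified statement.

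Three stronger readings are tempting, and the documents do not support them:
- A reader might infer that the Table 3 safeguard has nothing behind it in the criteria. It does: 5.1(c) and 5.2.4(c) bar clinically significant transaminase abnormalities.
- A reader might infer that entry rests on a single person's opinion. The criteria assign the judgement to no one person, and the schedule of activities places the inclusion/exclusion check on Day -1 of Period I, after screening.
- A reader might count the interval between the screening sample and the next scheduled liver test as part of the problem. That interval comes from the visit schedule, not from the wording of the criteria, and the fix would not change it.

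**Conclusion.** The mismatch is real but limited. The stated safeguard reaches the entry rules in weaker form, and the sponsor's own ALT/AST limits do not bind at entry.

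The people affected are candidates with screening ALT above 82 (men) or 56 (women) U/L, or AST above 73 or 46 U/L, whose values are judged clinically insignificant or acceptable. This takes Section 10.6 as the meaning of *abnormal*, which is very probable but not stated. How many such candidates there would be cannot be derived from the documents.

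The safety stake is small. Each dose is a single 400 mg tablet, hepatic disease and positive hepatitis serology are excluded, liver tests precede Periods II, III and IV, and Section 7.1.4.1 bars restart once liver stopping criteria are met. There is no effect on the bioequivalence analysis or power. The change is worth considering because it is cheap and delivers a protection that the protocol already claims.

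**What to change.** 1. Add an item to Section 5.2.4 excluding candidates whose screening ALT or AST, after any repeat, is above the Section 10.6 limits.
2. State in Section 8 item i that the reviewer's finding of clinically insignificant or acceptable does not override this exclusion.
3. In Table 3, cite the new criterion as the meaning of *abnormal*.

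Adding the qualifier *clinically significant* to Table 3 would make the texts agree, but only by lowering the stated safeguard to what the criteria already do. It is not enough by itself.

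The cost is protocol wording and possibly a few more screen failures among healthy volunteers. Sample size, visit schedule and analysis stay as they are.
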